# 7.2 Linac-based SBRT Treatment Delivery

Patients will receive 5 fractions of 5 Gy or 6.6 Gy delivered over a five-day period, as delineated above, based on whether or not they have received prior radiation therapy to the pancreatic region. Treatment may be delivered over 2 weeks, provided that the patient receives at least 2 fractions per week. Initial patient positioning will be based on volumetric kV (cone-beam CT) imaging with shifts to bony anatomy as appropriate. Orthogonal kV/MV or kV/kV projection imaging will be used to verify the location of the fiducials prior to delivery of the first treatment beam. A secondary shift based on the location of fiducials may be utilized, as indicated by the position of the fiducials. For free-breathing treatments, kV fluoroscopic images should be obtained to confirm the anticipated position of these fiducials during the entire respiratory cycle. Active monitoring of treatment delivery accuracy will be accomplished using kV and/or MV projection imaging, either immediately before or during all (or a subset of) treatment fields. Patient-

specific dosimetric quality assurance (QA) will be performed as per standard practice in the Department of Radiation Oncology, Indiana University School of Medicine.

# 7.3 Follow-Up

Following Linac-based SBRT, all patients will be monitored clinically and with serial imaging (CT scans and/or PET/CT if possible and as deemed necessary by the treating physician). A detailed medical history with physical examination and quality of life assessment will be performed at 4-6 weeks, 4 months, 6 months, 9 months and 1 year after radiation treatment. In years 2-5, the follow up interval will be every 3-6 months, as determined by the principal investigator. Follow up intervals may also be more frequent as indicated clinically. A complete blood count (CBC) with differential, comprehensive chemistry panel, tumor marker studies, and quality of life assessment will be performed at each follow-up interval.

We estimate that most patients will remain a subject in this study for approximately one year. Patients will remain enrolled on this protocol for a maximum of 5 years or until patient withdrawal. Patients that have completed the 5 year follow-up will continue being followed for survival information until death. The administration of subsequent chemotherapy and/or other antineoplastic treatment following Linac-based SBRT will be at the discretion of each patient's attending medical oncologist. If participants become very ill and cannot travel to IU for follow-up appointments, the study team will mail Quality of Life Questionnaires and request relevant medical records from local providers. This situation is expected due to progression profile, and if all protocol parameters are met, will not constitute a protocol deviation.

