# 8. TOXICITIES TO BE MONITORED/DOSAGE MODIFICATIONS

It is difficult at this time to predict with confidence the percentage risk of complications from the proposed Linac-based SBRT treatment. However, it is reasonable to extrapolate from the current experience with radiotherapy in and around the pancreas. Based upon prior phase I and phase II studies, we anticipate that the toxicities associated with this treatment will be acceptable. We estimate that ≤20% of patients will experience grade 2 or higher late Radiation-related GI toxicity within one year. Late GI toxicities are those events occurring more than 3 months after Linac-based SBRT. Acute GI toxicities are those events occurring within 3 months following Linac-based SBRT. Acute toxicities commonly associated with such treatment include nausea, vomiting, fatigue, anorexia and weight loss. Severe side effects such as gastrointestinal (GI) obstruction, perforation, or hemorrhage are uncommon complications, occurring in <5% of patients undergoing standard radiation therapy for pancreatic cancer. The major serious toxicity in this group of patients is the development of duodenal/gastric ulcers. Most of these are successfully managed medically. However, Stanford has observed 2 cases of duodenal perforation associated with Linacbased SBRT. We anticipate that because of refinements in radiation treatment planning techniques and because the dose will be divided over five treatments (as opposed to one), the biological equivalent and actual dose to the duodenum will be less than prior studies.

Although we expect a comparable rate of complications with fractionated Linac-based SBRT, it is important to note that vomiting, GI obstruction, GI hemorrhage, anorexia and weight loss are also commonly associated with pancreatic cancer progression. Clinical and radiographic assessments will be performed in an effort to identify these effects, ascertain their etiology and provide the most appropriate palliative measures. Hepatic and renal radiation toxicity is not anticipated given the expectation of limited incidental irradiation of these organs and we have not observed any to date in the patients treated with Linac-based SBRT. Complications, if any, will be graded according to the CTCAE, National Cancer Institute, version 4.0 (see Appendix I). We will also utilize the RTOG scale for grading acute and chronic radiotherapy toxicities.

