# 9. STUDY PARAMETERS/CALENDAR

	Pre-Study 	Treatment		Follow-Up 					
		Week 1	Week 2	4-6 weeks 	3 months	6 months	9 months	12 months	Yrs 2-5
Initial Consult	X								
Demographics	X								
History/Physical	X	X 	X 	X	X	X	X	X	Q6 months
Informed Consent	X								
Biopsy confirmation of adenocarcinoma	X								
CBC with differential	X	X	X	X	X	X	X	X	Q 6 months
CMP	X	X	X	X	X	X	X	X	Q 6 months
CA 19-9	X			X	X	X	X	X	Q 6 months
Negative Pregnancy Test 	X								
Fiducial Placement	X								
Simulation Scan	X								
SBRT		X	X						
Radiographic Eval 	СТ			СТ	СТ	СТ	СТ	СТ	CT
QoL/Pain Questionnaires	X	X	X	X	X	X	X	X	Q 6 months
AE Evaluation				X	X	X	X	X	Q 6 months

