#### Footnotes:

- Within 45 days of commencing study treatment.
- Urine or serum pregnancy test must be negative in all premenopausal women who have not undergone surgical sterilization procedures.
- FDG PET scan optional at baseline and at all follow-up intervals.
- All follow-up visits subsequent to the 4-6 week visit may be completed at an outside hospital. However, all records and imaging (copies of images in addition to reports) must be reviewed at IU. Follow-up appointments have a 30-day tolerance window. QoL surveys may be returned by mail for patients who are completing follow-up visits at an outside clinic.
- A treatment evaluation will be done in lieu of history/physical exam at these visits.
-  Surgical oncology visit note is acceptable if patient has undergone surgical procedures and is limited to travel to clinic

Protocol Version Date: 07/02/2024 Page 18

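### Section 7.3 places the second follow-up visit and its blood count at 4 months, the Section 9 calendar places it at 3 months, and the primary acute-toxicity window closes at 3 months

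*Combined protocol and SAP*

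**What the plan says.** Section 7.3 (Follow-Up) sets the first-year schedule: history, physical examination and "quality of life assessment will be performed at 4-6 weeks, 4 months, 6 months, 9 months and 1 year after radiation treatment". It adds that "A complete blood count (CBC) with differential, comprehensive chemistry panel, tumor marker studies" and a further quality of life assessment are done at every follow-up. Under 7.3 the second post-treatment blood count is therefore due at 4 months. The section also allows extra visits: "Follow up intervals may also be more frequent as indicated clinically".

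The Section 9 calendar has follow-up columns at 4-6 weeks, 3, 6, 9 and 12 months. The rows "CBC with differential", "QoL/Pain Questionnaires" and "AE Evaluation" are all marked in the 3-month column. Blood counts are also marked in treatment weeks 1 and 2. Footnote 4 to the calendar states: "Follow-up appointments have a 30-day tolerance window".

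The 3-month limit comes from several places. Section 8 states: "Acute GI toxicities are those events occurring within 3 months following Linac-based SBRT". Sections 3.1, 11.5 and 11.9 define the primary outcome over the same 3 months and name hematologic as well as GI toxicity. Section 3.3.2 makes pain at one and three months a main outcome. Section 15.3 has acute adverse events recorded for at least 90 days after treatment ends.

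**The concern.** The two schedules agree on every first-year visit except the one nearest the end of the primary outcome window. Both are current text, and nothing ranks one above the other.

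Hematologic toxicity is one of the two named components of the primary outcome. A symptomatic GI event can be recovered from the history at a later visit. A cytopenia that shows only in the laboratory can be graded only if blood is drawn while it is present. Under 7.3, no blood count is scheduled between the 4-6 week visit and a date about a month after the window closes. Under the calendar, a count is scheduled at the window's end. If staff follow different sections, patients are measured on different schedules for the same primary rate.

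The analysis plan does not repair this. Section 11.1 says missing data are not imputed. Section 11.9 gives no rule for a patient without a count late in the window. The late-toxicity objective in 3.2 and its analysis in 11.10 cover GI events only, so a cytopenia first found at month 4 enters neither the primary outcome nor that analysis.

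**Working it through.** The plan gives no figure to reproduce here. The check sets the two schedules side by side and converts them to days.

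**Schedules compared**

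| Visit | Section 7.3 | Section 9 calendar |
|---|---|---|
| First | 4-6 weeks | 4-6 weeks |
| Second | 4 months | 3 months |
| Third | 6 months | 6 months |
| Fourth | 9 months | 9 months |
| Fifth | 1 year | 12 months |

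**Nominal days.** Calendar months were added to each of 1,461 consecutive treatment-end dates.

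- Treatment end + 3 months: day 89 to 92, mean 91.3.
- Treatment end + 4 months: day 120 to 123, mean 121.7.
- Difference: 28 to 31 days, mean 30.4.
- 4-6 weeks: day 28 to 42.

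**Interval between the first and second follow-up blood counts.** With an average month of 365.25/12 = 30.4375 days, 3 months = 91.3 days and 4 months = 121.75 days.

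- Section 7.3: 121.75 − 42 = 79.75 to 121.75 − 28 = 93.75, about 80-94 days.
- Calendar: 91.3 − 42 = 49.3 to 91.3 − 28 = 63.3, about 49-63 days.

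**Effect of the tolerance.** The direction of the 30 days is not stated, so plus or minus 30 is assumed.

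- 3-month target: 91.3 ± 30 = day 61 to 121. The share inside the window is (91.3 − 61.3)/60 = 50%, or (90 − 61.3)/60 = 48% if the window ends at day 90.
- 4-month target, if the same tolerance is applied to it: 121.75 ± 30 = day 92 to 152. None of this lies inside a window ending at day 90 or day 91.3. With 30-day months the earliest permitted visit would be day 120 − 30 = 90, exactly at the limit.
- First visit at its latest: 42 + 30 = day 72, still inside the window under either schedule.

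**Other assessments at this visit.** Section 7.3 covers quality of life, blood count and chemistry. The pain questionnaire and adverse event evaluation are placed at visits only by the calendar. They move to month 4 only if a site takes 7.3 as governing the whole visit. In that case the 3-month pain outcome in 3.3.2 has no matching visit.

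**The case against.** The case for treating this as slight has real content.

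- **Other counts lie inside the window.** The calendar schedules blood counts in treatment weeks 1 and 2, and both schedules have one at 4-6 weeks. Hematologic monitoring is not absent; one scheduled count moves.
- **The exposure is narrow.** An event is lost only if it is a laboratory-only cytopenia of grade 3 or worse that arises after the 4-6 week count, resolves before month 4 and prompts no extra visit. The GI component is little affected, because Section 15.3 requires acute events to be recorded whatever the visit date.
- **The 4 months is probably a slip.** The primary objective, the pain outcome, Section 8, the calendar and Sections 11.5 and 11.9 all use 3 months, and Section 15.3 uses 90 days. Section 12 also mentions an electronic calendar of events, whose content is not shown.
- **Reconciling the text does not guarantee a count inside the window.** On the assumed tolerance, about half of the permitted range for a 3-month visit falls after it.

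All four bear on weight and stand to that extent. None removes the contradiction. A probable slip in an operative section can still be followed as written. The safeguards capture events that are noticed; they do not schedule a blood draw in the second half of the window. The tolerance does not reconcile the sections either, because it moves with whichever target date is used.

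**Conclusion.** The inconsistency is confirmed and should be corrected. The second follow-up visit differs by 28-31 days between 7.3 and the calendar. On nominal dates, following 7.3 makes the 4-6 week count (day 28-42) the last scheduled one inside the primary window and lengthens the gap to the next count from 49-63 to 80-94 days. The statements about permitted visit ranges rest on reading the tolerance as plus or minus 30 days.

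The textual conflict is certain. Its effect on the primary estimate is not known. The documents give no rate of events arising between week 6 and month 3, so no bias or count of missed events can be stated. The calendar does not fully secure a count inside the window, but it centres the visit on the window's end.

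**What to change.** Reconcile Section 7.3 with the Section 9 calendar so that a single second-visit time applies to every patient. Align it with the 3-month endpoints in 3.1, 3.3.2 and 11.9, and place the blood count, chemistry, adverse event evaluation and quality of life and pain questionnaires at that one visit.

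The cost is protocol wording only. Both sections already have one visit at this point, so none is added.

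A minor, separate correction can go in the same amendment: 3.3.1 names grade 3 alone, whereas 3.1, 11.5 and 11.9 also include higher grades. Bring 3.3.1 into line. This does not alter the analysis in 11.9.

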# 7.4 General Concomitant Medication and Supportive Care Guidelines

#### 7.4.1 Antidiarrheals and Anti-Emetics

For symptoms of diarrhea and/or abdominal cramping, patients will be instructed to take over-the-counter anti-diarrheal medication (loperamide). Additional antidiarrheal therapies may be used at the discretion of the treating physician. Patients should be instructed to increase fluid intake to help maintain fluid and electrolyte balance during episodes of diarrhea. Prophylactic anti-emetics (generally ondansetron, unless patient has intolerance/allergy) will be encouraged one hour prior to Linac-based SBRT and for up to 5 days following Linac-based SBRT on an as-needed basis. Additionally, patients will be instructed to increase fluid intake. All patients will be prescribed proton pump inhibitors (PPIs), which should begin by the start of Linac-based SBRT and continue for a minimum of 6 months following Linac-based SBRT.

#### 7.4.2 Other Concomitant Medications

Therapies considered necessary for the patient's well-being may be given at the discretion of the investigator. Other concomitant medications should be avoided except for analgesics, chronic treatments for concomitant medical conditions, or agents required for life-threatening medical problems. Specifically, if the patient is being treated with chemotherapy, it is recommended that chemotherapy be discontinued at least one week prior to initiation of Linac-based SBRT and that resumption of chemotherapy be delayed for at least one week following the conclusion of Linac-based SBRT. In general, prescription of these medications will be presided over by the patient's attending medical oncologist.

# 7.4.3 Use of Radioisotopes/Rad Machines

Stereotactic radiotherapy treatments will be delivered using a linear accelerator ("linac"). The radiation treatment plan will be designed to use multiple beams of radiation to concentrate large doses of radiation within a tumor. Cone beam CT imaging and diagnostic-energy (kV) imaging will be used to deliver image-guided radiation therapy (IGRT). IGRT allows delivery of highly accurate, stereotactic radiation treatment. The use of cone beam CT images during IGRT is considered standard of care. Uncertainties in tumor location are minimized because these machines have on-board, volumetric imaging for accuracy in initial patient setup; kV and MV projection imaging during treatment is used to monitor delivery accuracy and/or make corrections to the patients' position. The radioactive tracer FDG will be used to perform PET scans (when available), a special imaging procedure. Positron emission tomography (PET) is a type of nuclear medicine examination, which is based on the administration of a small amount of a radioactive FDG agent. The tracer (FDG) is a modified form of glucose, a sugar normally found in the bloodstream and used by cells in the body for energy. FDG is eliminated in the urine. With special imaging equipment, it is possible to detect radiation from the administered radioactive agent and obtain images of the body.

# 8. TOXICITIES TO BE MONITORED/DOSAGE MODIFICATIONS

It is difficult at this time to predict with confidence the percentage risk of complications from the proposed Linac-based SBRT treatment. However, it is reasonable to extrapolate from the current experience with radiotherapy in and around the pancreas. Based upon prior phase I and phase II studies, we anticipate that the toxicities associated with this treatment will be acceptable. We estimate that ≤20% of patients will experience grade 2 or higher late Radiation-related GI toxicity within one year. Late GI toxicities are those events occurring more than 3 months after Linac-based SBRT. Acute GI toxicities are those events occurring within 3 months following Linac-based SBRT. Acute toxicities commonly associated with such treatment include nausea, vomiting, fatigue, anorexia and weight loss. Severe side effects such as gastrointestinal (GI) obstruction, perforation, or hemorrhage are uncommon complications, occurring in <5% of patients undergoing standard radiation therapy for pancreatic cancer. The major serious toxicity in this group of patients is the development of duodenal/gastric ulcers. Most of these are successfully managed medically. However, Stanford has observed 2 cases of duodenal perforation associated with Linacbased SBRT. We anticipate that because of refinements in radiation treatment planning techniques and because the dose will be divided over five treatments (as opposed to one), the biological equivalent and actual dose to the duodenum will be less than prior studies.

Although we expect a comparable rate of complications with fractionated Linac-based SBRT, it is important to note that vomiting, GI obstruction, GI hemorrhage, anorexia and weight loss are also commonly associated with pancreatic cancer progression. Clinical and radiographic assessments will be performed in an effort to identify these effects, ascertain their etiology and provide the most appropriate palliative measures. Hepatic and renal radiation toxicity is not anticipated given the expectation of limited incidental irradiation of these organs and we have not observed any to date in the patients treated with Linac-based SBRT. Complications, if any, will be graded according to the CTCAE, National Cancer Institute, version 4.0 (see Appendix I). We will also utilize the RTOG scale for grading acute and chronic radiotherapy toxicities.

# 9. STUDY PARAMETERS/CALENDAR

	Pre-Study 	Treatment		Follow-Up 					
		Week 1	Week 2	4-6 weeks 	3 months	6 months	9 months	12 months	Yrs 2-5
Initial Consult	X								
Demographics	X								
History/Physical	X	X 	X 	X	X	X	X	X	Q6 months
Informed Consent	X								
Biopsy confirmation of adenocarcinoma	X								
CBC with differential	X	X	X	X	X	X	X	X	Q 6 months
CMP	X	X	X	X	X	X	X	X	Q 6 months
CA 19-9	X			X	X	X	X	X	Q 6 months
Negative Pregnancy Test 	X								
Fiducial Placement	X								
Simulation Scan	X								
SBRT		X	X						
Radiographic Eval 	СТ			СТ	СТ	СТ	СТ	СТ	CT
QoL/Pain Questionnaires	X	X	X	X	X	X	X	X	Q 6 months
AE Evaluation				X	X	X	X	X	Q 6 months

#### Footnotes:

- Within 45 days of commencing study treatment.
- Urine or serum pregnancy test must be negative in all premenopausal women who have not undergone surgical sterilization procedures.
- FDG PET scan optional at baseline and at all follow-up intervals.
- All follow-up visits subsequent to the 4-6 week visit may be completed at an outside hospital. However, all records and imaging (copies of images in addition to reports) must be reviewed at IU. Follow-up appointments have a 30-day tolerance window. QoL surveys may be returned by mail for patients who are completing follow-up visits at an outside clinic.
- A treatment evaluation will be done in lieu of history/physical exam at these visits.
-  Surgical oncology visit note is acceptable if patient has undergone surgical procedures and is limited to travel to clinic

Protocol Version Date: 07/02/2024 Page 18

#### 10. CRITERIA FOR EVALUATION/REMOVAL FROM STUDY

# **10.1** Anti-Tumor Effect and Response Evaluations

Patients will be evaluated for anti-tumor effect by follow-up imaging (pancreas protocol CT and/or PET-CT imaging) as outlined above. All subsequent scans (post-treatment) will be compared to the same pretreatment CT or PET/CT that was performed for radiation treatment planning. Evaluation of pancreatic and periampullary tumor response will be based on standard radiographic criteria for the treated lesion and will be prospectively recorded in the study database. Radiographic response of the pancreatic or periampullary tumor by diagnostic CT scans will be defined according to RECIST criteria as described below:

- CR = complete disappearance of index lesion
- PR = at least 30% decrease in the longest diameter of the index lesion PD = more than 20% increase in the longest diameter of the index lesion SD = does not meet criteria for PR or PD
- Local tumor progression will be defined as >=20% increased size on CT scan compared to a CT scan from prior to treatment.
- Distant progression will be defined as any new tumor found outside of the pancreas or periampullary region on CT scan.

Pancreatic or periampullary tumor response will also be assessed by FDG-PET scans (when available) according to the following criteria:

- CR = target lesion becomes photopenic or standardized uptake value (SUV) ratio of tumor/liver less than or equal to 1
- PR = decrease in SUV ratio of tumor/liver (at least 30%) PD = increase in SUV ratio of tumor/liver (at least 20%)
- SD = no significant change in SUV ratio of tumor/liver

We will also determine PET response (in those patients who have undergone follow-up FDG PET scanning) with the new PERCIST criteria as reported by Wahl et al., defined as follows: (33)

- Complete metabolic response (CMR): complete resolution of 18F-FDG uptake within the measurable target lesions so that it is less than mean liver activity and indistinguishable from surrounding background blood-pool levels with no new 18F-FDG avid lesions
- Partial metabolic response (PMR): reduction by a minimum of 30% in the target lesion's 18F-FDG peak
- Stable metabolic disease (SMD): disease other than CMR, PMR, or progressive metabolic disease
- Progressive metabolic disease (PMD): 30% or greater increase in 18F-FDG peak in the target lesion or the development of new 18F-FDG avid lesions that are typical of cancer.

Patients' responses to therapy will also be evaluated clinically after completion of their Linac-based SBRT. The following are clinical definitions for response:

• CR = complete alleviation of pain or other symptoms thought to be related

- to the index lesion
- PR = improvement, but not complete elimination, of pain or other symptoms thought to be related to the index lesion
- PD = worsening of pain or other symptoms thought to be related to the index lesion
- SD = does not meet criteria for PR or PD

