# 2.3 Rationale for Selection of Patient Population

As noted previously, local control rates remain unsatisfactory in patients with unresectable pancreatic cancer, up to 30% of whom die with uncontrolled local disease. Local progression of pancreatic cancer can cause distressing symptoms including pain, biliary and gastrointestinal tract obstruction, and pancreatic insufficiency. Furthermore, preliminary data suggest that some patients treated with stereotactic body radiation therapy for unresectable disease achieve sufficient tumor response to proceed to surgical resection; (20) in patients with borderline resectable disease, neoadjuvant SBRT has also been associated with high rates of margin-negative resection. (21)

The development of recurrent pancreatic cancer after definitive treatment with surgery, radiation, chemotherapy, or a combination of these universally portends a dismal prognosis, with the 5-year survival for such patients being 5.6% or less. (24) Unfortunately, this scenario is not uncommon; even among the small number of patients (10-15%) able to undergo potentially curative surgical resection, more than 80% subsequently develop recurrent disease.(25) Following resection, 71-77% develop distant metastases within 2 years, often accompanied by concurrent locoregional recurrence, while up to 30% exhibit isolated locoregional recurrence. (26-29) Patients who develop combined distant/locoregional recurrence have a median survival of 3 months from the time of recurrence, while those with isolated locoregional recurrence have a median survival of 7 months. (28) Locoregional recurrence is, therefore, a common and serious problem both in the setting of metastatic disease and as an isolated entity. Symptomatic manifestations include pain, gastric outlet/small bowel obstruction, portal hypertension, biliary obstruction, and malnutrition. Although survival is determined chiefly by systemic disease control, local control greatly affects quality of life in pancreatic and periampullary cancer patients. (29, 30) Among the majority of patients with pancreatic cancer who present with unresectable disease, chemoradiation is able to transiently stabilize the disease in some patients and to prolong median survival to 8-14 months. (8, 9, 31) Regardless of whether a tumor is resectable or unresectable at diagnosis, the symptoms associated with local recurrence or persistence of disease require swift and effective treatment.

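### Local progression is judged only against the pretreatment scan, so regrowth after a response is recorded late or missed, and tumor returning in the treated bed has no CT rule of its own

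*Combined protocol and SAP*

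**What the plan says.** Section 10.1 fixes one reference scan for the whole of follow-up: "All subsequent scans (post-treatment) will be compared to the same pretreatment CT or PET/CT that was performed for radiation treatment planning". The endpoint definition agrees with it: "Local tumor progression will be defined as >=20% increased size on CT scan compared to a CT scan from prior to treatment".

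The CT response categories concern the index lesion only: "CR = complete disappearance of index lesion", "PR = at least 30% decrease in the longest diameter of the index lesion" and "PD = more than 20% increase in the longest diameter of the index lesion". None names a different reference scan. New tumor on CT appears only in the definition of distant spread: "Distant progression will be defined as any new tumor found outside of the pancreas or periampullary region on CT scan".

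Local progression is a secondary objective in section 3.2. Section 11.10 analyzes time to local progression by Kaplan-Meier in Cohort B, with a median, a 1-year rate and 90% intervals. Section 10.2 defines PFS, local PFS and duration of response, all of which use progression as an event. It gives no separate definition of time to local progression, so the wording in 10.1 is the only one available for that endpoint.

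Two places touch on surgery after SBRT. The background in section 2.3 reports that some patients treated in earlier work "achieve sufficient tumor response to proceed to surgical resection". Footnote 6 to the section 9 calendar, attached to the 4-6 week visit, says: "Surgical oncology visit note is acceptable if patient has undergone surgical procedures". Sections 10.1, 10.2 and 11.10 give no rule for resection as an event, a censoring point or a new baseline.

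**The concern.** A fixed pretreatment reference works for a tumor that never shrinks. For one that does shrink, the distance between its smallest size and the progression threshold widens with the depth of response. The patients with the best response therefore have the most room to fail locally before the failure is recorded.

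There is a second gap. Tumor that reappears in the pancreas or treated bed is not distant progression, because that definition covers only sites outside the region. It is not local progression either until it passes a size threshold tied to the earlier lesion. Between those two rules, a visible local recurrence on CT can have no endpoint category.

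At stake are the local control estimates: time to local progression and its 1-year rate in Cohort B first, then the composite endpoints that include progression. Compared with a rule based on the smallest size, the present rule can only give the same date or a later one, so any bias favors local control.

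**Working it through.** The plan states no assumed rate, power or precision for local progression, so there is no figure of its own to reproduce.

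**Inputs from the documents.** Progression threshold 1.20 times the pretreatment size, and partial response at 0.70 times or less (10.1). About 30 patients in Cohort B (11.5). Tumors under 8.0 cm at planning (4.1). CT at 4-6 weeks and at 3, 6, 9 and 12 months (section 9). I read size in the progression rule as longest diameter, as in the response categories.

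**Assumed, because the documents are silent.** Shrinkage other than 30%, volume doubling time, true local control rate, and number of delayed events.

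**Step 1: growth needed from the smallest size.** With pretreatment diameter D and shrinkage s, the smallest size is (1 − s)D. The plan's event is at 1.20D. An event measured from the smallest size would be at 1.20(1 − s)D. Growth needed under the plan is 1.20/(1 − s) − 1.

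| Shrinkage s | Event if measured from smallest size | Event under the plan | Growth from smallest size needed under the plan |
|---|---|---|---|
| 0% | 1.20D | 1.20D | 20% |
| 10% | 1.08D | 1.20D | 33% |
| 20% | 0.96D | 1.20D | 50% |
| 30% | 0.84D | 1.20D | 1.20/0.70 − 1 = 71% |
| 50% | 0.60D | 1.20D | 1.20/0.50 − 1 = 140% |

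For a sphere, the 30% case is 1.714³ = 5.0-fold growth in volume.

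**Step 2: the gap as time.** The gap between the two event sizes, in volume doublings, is 3 × log2(1/(1 − s)): 1.54 at 30% shrinkage and 3.0 at 50%. With assumed doubling times of 60, 120 or 180 days, 1.54 doublings take about 3.0, 6.1 or 9.1 months (for example 1.54 × 60/30.4 = 3.0). From month 3 the first-year scans are three months apart, so this is roughly one to three scheduled scans.

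**Step 3: complete response or resection.** If the rule is applied literally, a recurrence must reach 1.20 times the earlier diameter: 4.8 cm after a 4.0 cm tumor, about 9.5 cm after a 7.9 cm tumor (1.20 × 7.9 = 9.48). Below that size it meets neither the local nor the distant CT definition.

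**Step 4: effect on the 1-year rate.** With 30 patients and no censoring, each local failure missed or pushed past one year adds 1/30 = 3.3 points to the local-progression-free rate.

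| Assumed true rate (events) | 90% exact interval at the true rate | 1 delayed | 3 delayed | 5 delayed |
|---|---|---|---|---|
| 60% (12) | 43-75% | 63% | 70% | 77% |
| 80% (6) | 64-91% | 83% | 90% | 97% |

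One or three delayed events leave the estimate inside the interval around the true rate; five move it outside in both rows. The documents do not say which number is realistic.

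**The case against.** **Late is not the same as never.** A reader might infer that regrowth after response is simply not counted. The text does not support that. Regrowth counts once it reaches 120% of the pretreatment size. It is missed only if death or the end of follow-up comes first, and for local PFS a death is itself an event. This stands, and it limits the point to delay with some loss.

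**Other progression categories exist.** Section 10.1 also defines progression by PET uptake ratio and by PERCIST, which counts new FDG-avid lesions, and adds a category based on symptoms. Section 10.3 provides independent radiology review and review by the principal investigator. But PET is optional under the section 9 footnotes, none of these categories is tied to local progression, and reviewers still need a definition to apply. This narrows the gap without closing it. The RECIST label does not close it either, because 10.1 writes out its own criteria and its own reference scan.

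**The PFS effect is uncertain.** Section 10.2 asks for documented local, regional or distant progression and does not cite the 20% rule. A bed recurrence could be accepted under that wording. Duration of response ends at the first sign of local progression, which is equally open. Distant progression and death will also set many PFS dates. All of this stands.

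**Resection is only lightly foreseen.** The statement in 2.3 is background from earlier studies, and footnote 6 mentions surgical procedures without saying resection. Resection after SBRT is not a study procedure or endpoint. For resected patients, the fair reading is a case the rule does not address, rather than a rule that expressly disregards their recurrences.

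**The stakes are limited.** This is a pilot safety study. Local progression is estimated descriptively with no threshold to pass, and it does not appear among the secondary outcome measures in 3.3.2. That argues for a modest priority.

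**Conclusion.** The point holds as a defect in a secondary endpoint definition. The pretreatment reference is explicit and stated twice, nothing resets it, and no CT rule covers new or reappearing tumor in the treated region. For responders who regrow, the threshold is 71% growth from the smallest size after 30% shrinkage and 140% after 50%. For complete response or resection, the documents leave bed recurrence without a CT definition below 120% of the pretreatment size.

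The consequence is a possible overstatement of time to local progression and of the 1-year local-progression-free rate in Cohort B, at 3.3 points per delayed or missed event among 30 patients without censoring. Local PFS, PFS and duration of response may be affected to a lesser and less certain degree.

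A reader might go further and conclude that local control will be overstated by a material amount. The documents do not support that. They give no response, resection or regrowth rates for this trial, and the scenarios above rest on assumed rates and counts. If few patients respond and then fail locally, the effect is negligible. Overall survival, the primary toxicity endpoint, the sample size and the stopping rule are untouched.

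**What to change.** - In 10.1, define local progression as at least 20% growth in longest diameter over the smallest size recorded since and including the pretreatment scan, or any new or reappearing tumor in the treated bed or region after complete response or resection.
- In 10.2 and 11.10, state how resection enters the time-to-event analyses, for example with the first post-operative scan as the new baseline, and say that PFS, local PFS and duration of response use the same definition.
- Report the pretreatment-referenced version as a sensitivity analysis, so that the effect of the change is visible.
- While editing, align the two thresholds (more than 20% for PD, at least 20% for local progression), and say what applies when no measurable baseline lesion exists. Section 4.1 allows recurrence to be diagnosed on rising CA19-9, so that case is possible.

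The change needs no extra scans. CT is already scheduled at each follow-up visit, and images taken elsewhere must be reviewed centrally at the study site. The cost is redrafting and some re-reading of scans against the smallest size. The real downside is some earlier progression calls from post-radiation size variation, which the sensitivity analysis would show.
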